### 1. Administrative Information

# 1.1. Study identifiers

- Research Ethics Approval- University of Pretoria, Humanities Research Ethics (Approval Number: HUM07/0322).
- Clinical trial registry- clinicaltrials.gov (Identifier: NCT05337748)

# 2. Study site and investigators

# 2.1. Study site

The study will be conducted at the Department of Speech-Language Pathology and Audiology, University of Pretoria, [name]

Reasons for site selection:

- It is a widely recognized research institution in the field of audiology and is the leading African research institution in audiology. Furthermore, the site is designated as the only official World Health Organization Collaborating Center for the Prevention of Deafness and Hearing Loss in Africa.
- In terms of the clinical population served at the university clinic, the racial diversity largely reflects the US population in terms of an English-speaking majority white population (Census.gov) (1). 78% of participants in this study represented a white only adult group compared to 76% in the general US population (Census.gov) (1).

# 3. Introduction and study objective

Hearing loss is a highly prevalent condition, with numerous debilitating consequences when left untreated. However, less than 20% of adults with hearing loss in the United States use hearing aids. Over-the-counter (OTC) hearing aids became available in October 2022 to improve access and affordability. However, clinical effectiveness studies of available OTC hearing aids using the existing devices in the market are limited. The Lexie Lumen hearing aid is a wireless self-fitting behind-the-ear hearing aid, coupled with a slimtube and dome, intended to amplify sound for individuals 18 years or older with a known or perceived mild to moderate hearing impairment. This type of OTC hearing aid functions in conjunction with a smartphone app, which allows for an in-situ hearing check to estimate hearing thresholds across various audiometric frequencies, and to program the hearing aids using a predetermined prescription formula.

### 3.1. Objective

To compare the clinical effectiveness of a self-fit OTC self-fitting hearing aid (Lexie Lumen) with remote support to a gold standard audiologist-fitted hearing.

# 3.2. Research Design and Interventions

[figure not shown]
This study will be done using a randomized control trial (RCT), conducted cross-sectionally (+- 45 days) to evaluate the effectiveness of the self-fit group to an audiologist-fit group.

# 3.2.1. SF arm (Intervention group)

In this study, the SF condition means that participants will be provided with the Lexie Lumen hearing aids and will be asked to set up and manage the devices using the Lexie app, entirely without professional support, as would be standard for this OTC model. Hearing aids will be provided in their standard, consumer packaging, including all labelling and instructional material. Furthermore, they will be fitted according to the proprietary fitting algorithm (Lexie Comfort) using the in-situ thresholds obtained via the Lexie app. The fitting algorithm will be based on National Acoustics Laboratories' Non-Linear Version 2 (NAL-NL2) , with additional adjustments aimed for a greater listening comfort.

# 3.2.2. Audiologist-fit arm (Control)

In the AF condition, participants will be provided with the same Lexie Lumen hearing aids fitted to match the National Acoustics Laboratories' Non-Linear Version 2 (NAL-NL2) acoustic gain prescriptions as closely as possible . AF fitting will be based on diagnostic audiometry conducted in a soundproof booth by the audiologist. Diagnostic audiometry will follow ISO 8253-1:2010 Acoustics — Audiometric test methods — Part 1: Pure-tone air and bone conduction audiometry guidelines. Participants in the AF group will be orientated on the use and management of the hearing aid by the audiologist.

**Figure 1.** Procedural description of the two groups of the randomized controlled trial. SF= self-fit; AF = audiologist fit.

The study will be conducted as two phases (four visits per participant). Phase I will be a two-week, take-home field trial after fitting the hearing aids. During the first 2-weeks no assistance or fine-tuning by the online Lexie hearing experts for the SF group will be allowed, and no fine-tuning by the audiologist in the AF group. This procedure will

be followed to isolate and only compare the benefit provided by the fitting without the help of online support or adjustment.

Phase II will commence at the first follow-up appointment on the third clinical visit. During this appointment, participants of the AF group will be allowed to request fine-tuning or assistance from the audiologist, if desired. The participants in the SF group will be informed that assistance could be sought through the Lexie online hearing experts, if desired. Phase II will be approximately 6 weeks in duration, and upon completion the final clinic visit and assessments will be conducted. Figure 2 provides an overview of the study protocol.

[figure not shown]

Figure 2. Trial timeline and design

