# 4.2.2. Digits-in-Noise

Since the QuickSIN was developed in American English, one concern was that South African participants could have difficulty recognizing the words due to differences in dialect. Therefore, in addition to the QuickSIN, speech-in-noise performance will be measured using the South African English Digits-in-Noise test (DIN) (5,6). The DIN unaided and aided results will be measured following the same procedure as set for performing the QuickSIN).

Table 1. Timing of the assessments						
Visit	Baseline	Hearing Aid Fitting	2-week follow- up	6-week follow- up		
Pure tone audiometry	Х					
APHAB	X		Х	X		
IOI-HA			X	X		
QuickSIN	X		Х	Х		
DIN	X		X	X		
Real-Ear Measurement		Х		Х		

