### Adverse events (Safety analysis)

Expected SAEs will be summarised as the number and proportion of patients experiencing at least one event. This will be done overall and by category. In addition, the total number of events will be reported.

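### A safety summary is planned but no visit asks about adverse events, and Phase II help contacts differ by arm, so event counts may be incomplete and not comparable between arms

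*Combined protocol and SAP*

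**What the plan says.** The safety paragraph of section 5.3 reads: "Expected SAEs will be summarised as the number and proportion of patients experiencing at least one event". It continues "This will be done overall and by category" and ends "In addition, the total number of events will be reported". It does not define the events, list the categories, name who records them, say when or how participants are asked, or mention a breakdown by arm.

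The visit schedule is in section 4.2.2 under "Table 1. Timing of the assessments". Its rows are pure tone audiometry, APHAB, IOI-HA, QuickSIN, DIN and real-ear measurement. None is an adverse-event item. Sections 4.1 and 4.2 describe no adverse-event question either.

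On contact during the trial, section 3.2.1 has self-fit (SF) participants set up and manage the device "entirely without professional support, as would be standard for this OTC model". Section 3.2.2 has the audiologist orientate audiologist-fit (AF) participants. For Phase I it says "During the first 2-weeks no assistance or fine-tuning by the online Lexie hearing experts for the SF group will be allowed", and it rules out audiologist fine-tuning in the AF arm. For Phase II, AF participants may request fine-tuning or assistance from the audiologist at the third-visit appointment, while for the other arm "The participants in the SF group will be informed that assistance could be sought through the Lexie online hearing experts, if desired". Section 3.4 states that the trial cannot be blinded.

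**The concern.** The plan commits to an analysis for which it describes no data collection. If nobody is scheduled to ask, an event enters the record only when a participant mentions it, or when a member of staff happens to enquire and write it down. In an open-label trial both can depend on who the participant is talking to and on the known allocation.

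In Phase II the person to whom a problem is naturally taken differs by arm. One is a member of the study team. The other is the product's online service, whose contacts with participants are not said to reach the study team.

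The trial asks whether a self-managed device can stand in for a professional fitting (section 3.1). A low or zero event count would be read as reassurance on that question, and it cannot be read that way if the enquiry was not made, or not made equally.

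**Working it through.** The plan states no safety figure that could be reproduced, so the main check sets its sections side by side.

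1. **Output promised.** Section 5.3 promises participants with at least one event (number and proportion, overall and by category) and a total event count.
2. **Data source.** Table 1 has six assessments over four visits and no adverse-event row. Sections 4.1 to 4.2 contain no question on adverse events, and section 5.4 (missing data) does not mention them. No source for the output in step 1 is stated.
3. **Contact routes.**

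| Period | AF arm | SF arm |
|---|---|---|
| Phase I (2 weeks) | No audiologist fine-tuning | No online expert assistance or fine-tuning |
| Third visit | May request help from the study audiologist | Attends; told that online experts are available |
| Phase II (about 6 weeks) | No between-visit contact described | Online experts; no stated route to investigators |
| Final visit | Assessments as in Table 1 | Assessments as in Table 1 |

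The routes differ mainly in Phase II. The two follow-up visits are common to both arms, but the plan does not use them to ask about events.

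4. **What unequal recording could do (illustration only).** The 30 per arm is from section 3.3. The true rate of 20% in both arms and the capture rates are assumptions, and a rate this high would suit minor device-related events rather than serious ones. Expected recorded participants = 30 × true rate × capture, with 30 × 0.20 = 6 truly affected per arm.

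| Capture, one arm / other arm | Recorded, one arm | Recorded, other arm | Apparent gap | Pooled, of 60 (true 20%) |
|---|---|---|---|---|
| 100% / 100% | 6.0 (20%) | 6.0 (20%) | 0 points | 12.0 (20%) |
| 90% / 60% | 6 × 0.9 = 5.4 (18%) | 6 × 0.6 = 3.6 (12%) | 6 points | 9.0 (15%) |
| 90% / 30% | 6 × 0.9 = 5.4 (18%) | 6 × 0.3 = 1.8 (6%) | 12 points | 7.2 (12%) |

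The columns are deliberately not labelled AF and SF. Exchanging the arms reverses the sign of the gap, and nothing in the documents says which way round it would be. The last column shows that a pooled count suffers too.

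5. **What a zero count would mean.** With 0 of n recorded, the one-sided 95% upper limit on the recorded rate is 1 − 0.05^(1/n), and the limit on the true rate is that value divided by capture.
   - One arm, n = 30: 1 − 0.05^(1/30) = 9.5% with full capture; 9.5% / 0.5 = 19.0% with an assumed 50% capture.
   - Both arms, n = 60: 1 − 0.05^(1/60) = 4.9% with full capture; 4.87% / 0.5 = 9.7% with an assumed 50% capture.

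**The case against.** The case for the plan has real weight. The documents are silent on how events are elicited; they do not say that participants will not be asked. Both arms attend the same four visits, which gives equal in-person opportunities to report. The sentence on the online experts concerns optional assistance, not event reporting. Section 5.3 refers to expected SAEs, and serious events are less likely to go unmentioned than minor ones. No between-arm safety comparison and no safety hypothesis is stated. Figures 1 and 2 are not available here, so the finding is limited to the text and Table 1.

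Most of this stands, and it limits the point to a risk. It does not remove the gap: shared visits make equal enquiry possible, but the plan does not schedule it, and a pooled summary also needs complete data.

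A reader might go further and infer that the self-fit arm has the weaker detection route and will look falsely safe. The documents do not support that. Help from the audiologist is described only at the third visit, which both arms attend. During the following six weeks the SF arm has a described contact channel and the AF arm has none. If the online experts' contacts were relayed, recording could be fuller in SF. Any specific false advantage for self-fitting would rest wholly on assumed capture rates that favour one direction.

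**Conclusion.** The point holds as a gap with a risk attached. A safety summary is promised, no visit in the text or Table 1 schedules the enquiry that would supply it, and Phase II help contacts differ by arm with no stated return route from the online experts. Event counts may therefore be incomplete and may not be comparable between arms. That they will be incomplete, or will differ by arm, is not shown.

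Direction and size are not established. The illustrated gaps of 6 and 12 points rest on an assumed 20% event rate and assumed capture rates, could fall either way, and vanish with equal capture. They matter for an arm comparison only if results are split by arm, which section 5.3 does not state. The APHAB, IOI-HA and speech-in-noise analyses are unaffected. The change is worth making because the safety summary cannot be interpreted without it and the visits needed already exist.

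**What to change.** - **Table 1:** add an adverse-event row at the 2-week and final visits.
- **Procedure:** ask the same open question and the same short checklist in both arms (for example ear pain, skin irritation, discharge, uncomfortable loudness, tinnitus, stopping wearing the device). Ask after APHAB and IOI-HA are complete, so that the primary outcome is not primed, and before any fine-tuning or discussion of support.
- **Section 5.3, safety paragraph:** define the events and categories. State that visit-elicited events, including non-serious device-related ones, are reported descriptively by arm. List events learned by other routes separately, including any reported by the online experts with the participant's permission.
- **Section 3.2.2:** state whether and how events that SF participants describe to the online experts reach the investigators.

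The cost is a few minutes at two existing visits and one form page. The link to the online experts also needs participant permission and an agreed process. Active questioning will raise the reported event count in both arms, and the report should say so. No visit, treatment or support rule changes.

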### 3.3. Sample size

This study aims to recruit 60 people (approximately 30 people in each group) with parallel allocation to the self-fit and audiologist fit groups. Sample size estimation is based on a previous OTC trial conducted by Sabin et al. 2020, who recruited similar sample sizes .

# 3.4. Randomization and blinding

Participants will be randomized into the self-fit or audiologist fit group using a random number generator. Due to the nature of the study and requirement for audiologist control over the settings in the audiologist-fit group, blinding will not be possible.

### 3.5. Participant eligibility criteria

### Inclusion:

- Adults >18 years old with a known or self-reported mild to moderate hearing impairment.
- Relatively high degree of English proficiency if English is not the participant's first language. This will be measured as per online English proficiency test (EF SET).
   A score of 51% or more, corresponding to an English B2 (upper-intermediate) level according to the Common European Framework Reference (CEFR) will be included.
- Access to or in possession of a smartphone.

### **Exclusion:**

History of outer or middle ear disease in the last 90 days.

### · Audiometric criteria:

- o Normal hearing bilaterally (PTA 0.5 to 4 kHz ≤ 20 dB HL)
- Severe hearing loss with any two frequencies at 0.5, 1, 2 and 4 kHz exceeding 80 dB HL
- Air-bone gaps of more than 20 dB HL at three or more frequencies (0.5 to 4 kHz) in either ear.

### 4. Outcome measures

# 4.1. Subjective outcome measures

Participants will report on overall hearing improvement by means of the following standardized questionnaires:

# 4.1.1. Abbreviated Profile of Hearing Aid Benefit (APHAB)

This questionnaire quantifies a wearer's self-reported difficulty with communication in everyday communication scenarios (2). Therefore, a representative and valid means of measuring the effectiveness of the study device.

Participants will complete this questionnaire unaided at the end of the first visit and then again at the end of the first and second field trials. Their responses are based on their experience with the study device.

# 4.1.2. International Inventory for Hearing Aids (IOI-HA)

Self-report questionnaires such as the IOI-HA determine wearer-oriented measures and assess how well a person believes their hearing problems have been addressed by means of the benefit derived from their hearing aids (3). Participants will complete this questionnaire at the end of the first and second field trials. Their responses are based on their experience with the study device.

### 4.2. Behavioral outcome measures

Participants of both groups will participate in the following speech recognition in noise assessments to be conducted as unaided at the pre-field trial stage and as aided at both the post-field trials.

### 4.2.1. QuickSIN

Several aspects of the QuickSIN test make it suitable for use in assessing comparable improvement of speech-in-noise performance. (1) It is designed to be presented above average conversational level (2) It uses a wide range of SNRs, and (3) the multi-talker background noise represents a common and challenging communication situation. QuickSIN is reported in terms of SNR loss, the increase in SNR required to understand speech in noise compared to persons with normal hearing; higher SNR loss indicates a poorer outcome (4).

SNR loss will be measured unaided at the initial assessment for all participants (prior to the random allocation process). Twice thereafter the aided SNR Loss will be measured. The first aided measurement as per initial fitting settings at the 3rd visit following the post 2-week field trial for the AF and SF groups. The second SNR loss will be measured with

the hearing aids set to the user's preferred setting at the 4th visit, post the 6-week field trial for both groups.

# 4.2.2. Digits-in-Noise

Since the QuickSIN was developed in American English, one concern was that South African participants could have difficulty recognizing the words due to differences in dialect. Therefore, in addition to the QuickSIN, speech-in-noise performance will be measured using the South African English Digits-in-Noise test (DIN) (5,6). The DIN unaided and aided results will be measured following the same procedure as set for performing the QuickSIN).

Table 1. Timing of the assessments						
Visit	Baseline	Hearing Aid Fitting	2-week follow- up	6-week follow- up		
Pure tone audiometry	Х					
APHAB	X		Х	X		
IOI-HA			X	X		
QuickSIN	X		Х	Х		
DIN	X		X	X		
Real-Ear Measurement		Х		Х		

# 4.3. Hypothesis

### Primary endpoint hypothesis:

*Null hypothesis:* No difference in self-reported hearing aid benefit (Abbreviated Profile of Hearing Aid Benefit) between the Lexie self-fit group (p0) and audiologist-fit (p1) group at 2-and 6-weeks from baseline, i.e., p1 = p0

Alternative Hypothesis (2-sided): The self-reported hearing aid benefit (Abbreviated Profile of Hearing Aid Benefit) of the Lexie self-fit group (p1) at 2- and 6- weeks will be non-inferior to the audiologist-fit group (p0), within 16.3 (smallest observable change for the APHAB), i.e., p0 – p1  $\leq$  16.3. The non-inferiority margin (- $\Delta$ NI) was arbitrarily decided and is defined as the degree of hearing benefit (%) change for the smallest observable change on the scales.

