### Secondary endpoint hypothesis:

*Null hypothesis*: No difference in self-reported benefit for the Lexie self-fit group (p1) at 2- and 6-weeks and audiologist fit hearing aids (p0) using the International Outcome Inventory for Hearing Aids (IOI-HA), i.e., p1 = p0

Alternative hypothesis (2-sided): The self-reported improvement (IOI-HA) of the Lexie self-fit group (p1) at 2- and 6-weeks will be non-inferior to the audiologist fit group, within 1 point on all scales (smallest observable difference on each scale). i.e.,  $p0 - p1 \le 1$ . This non-inferiority margin (- $\Delta$ NI) was decided based on the critical difference score reported for the IOI-HA  $^4$ .

*Null hypothesis:* No difference in speech recognition in noise (QuickSIN and DIN) improvement between the Lexie self-fit group and audiologist-fit group at 2- and 6- weeks), i.e., p1 = p0

Alternative hypothesis: The improvement of speech recognition in noise for the Lexie self-fit group at 2- and 6- weeks will be non-inferior to the audiologist-fit hearing aid using the QuickSIN and digits-in-noise test (DIN), within 1.8 dB SNR. The non-inferiority margin ( $-\Delta$ NI) is based on the critical difference score of the QuickSIN  $^5$ , i.e.,  $p0 - p1 \le 1.8$ .

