# 5. Statistical analyses

# 5.1. Level of statistical significance

Final analyses of the primary and secondary outcomes will be analysed using a two-sided significance level of 5%.

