# Self-reported hearing aid difficulties

Primary endpoint analyses include the self-reported benefit using the APHAB. Benefit is determined by calculating the APHAB scores conducted at the aided assessment (2-week and 6-week follow-ups) from the baseline scores. The primary endpoint data for all the scores measured at all time points (raw scores), along with the calculated benefit scores (unaided-aided) will be continuous variables. Data will be assessed for normality using the Shapiro Wilk's test. For non-normally distributed variables, non-parametric comparisons between groups will be completed using the Mann Whitney *U* test. For normally distributed variables, comparisons will be done using the independent samples *t*-test.

Effect sizes will be calculated for normally distributed variables, where differences were significant. Cohen's *d* is the primary metric for determining effect sizes of normally distributed variables, for which the values of 0.8, 0.5 and 0.2 are interpreted as large, medium and small effect sizes, respectively. The following formula will be used:

$$d = \frac{M1 - M2}{SDpooled}$$

Effect sizes for non-normally distributed variables will be calculated using effect size *r* for non-parametric tests, calculated using the following formula:

$$z/\sqrt{N}$$

IOI-HA (secondary endpoint) will be conducted at 2- and 6-weeks post hearing aid fitting. IOI-HA data are ordinal response categories and will, therefore, be analysed using non-parametric Mann Whitney U tests for comparison between the two groups.

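### The APHAB margin of 16.3 is not tied to audiologist-fit benefit, no confidence limit is compared with it, and no criterion asks whether self-fit improves on unaided hearing

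*Combined protocol and SAP*

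**What the plan says.** Section 4.3 (primary endpoint hypothesis) makes self-fit non-inferior to audiologist-fit on APHAB benefit at 2 and 6 weeks "within 16.3 (smallest observable change for the APHAB"). It adds that the margin "was arbitrarily decided and is defined as the degree of hearing benefit (%) change for the smallest observable change on the scales". No source is cited for the value. By contrast, the IOI-HA margin of 1 point "was decided based on the critical difference score reported for the IOI-HA", with a reference, and the 1.8 dB speech-in-noise margin is tied to a cited QuickSIN critical difference.

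Section 5.3 lists raw APHAB scores as primary endpoint data, "along with the calculated benefit scores (unaided-aided) will be continuous variables". The arms are compared by an independent-samples t-test or a Mann-Whitney U test, depending on a normality test. Section 5.1 sets two-sided 5% significance. Section 4.1.1 has participants complete the APHAB unaided at the first visit, so a baseline exists in both arms.

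On size, section 3.3 says: "This study aims to recruit 60 people (approximately 30 people in each group) with parallel allocation". It gives no SD, power or expected difference.

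**The concern.** A non-inferiority margin should be small relative to what the control achieves. Otherwise a new treatment that achieves nothing can sit inside it. The smallest observable change describes what the questionnaire can detect. It does not show that a mean loss of that size is acceptable, or that any benefit over unaided hearing is kept.

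Three gaps combine here. The margin is not set against audiologist-fit benefit. No decision rule connects the planned tests to the margin. No criterion concerns benefit over unaided hearing. If audiologist-fit benefit is well below 16.3 points, a conclusion of non-inferiority would be compatible with self-fit giving no benefit at all, and readers could still take it as evidence that the self-fit device works.

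**Working it through.** **The plan's own figure.** The 60 participants cannot be reproduced from inputs. The plan says "Sample size estimation is based on a previous OTC trial" and gives no SD or power. With margin 16.3, no true difference and one-sided 2.5%, 30 per arm corresponds to an SD of 16.3 / [(1.960 + 0.842) × √(2/30)] = 22.5 at 80% power, or 19.5 at 90%. Neither SD is in the documents.

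**Inputs**
- Margin M = 16.3 (section 4.3).
- n = 30 per arm (section 3.3), with no losses.
- Two-sided 5% (section 5.1), read as a 95% confidence interval.
- Assumed: SD of benefit 15, 20 or 25; true audiologist-fit benefit B from 5 to 20; true self-fit benefit 0.
- Assumed: non-inferiority is declared if the lower 95% limit for self-fit minus audiologist-fit is above −16.3. The plan does not state this rule.

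**Step 1: what passes when observed self-fit benefit is zero.** The half-width is t(0.975; 58) × SD × √(2/30). At SD 20 this is 2.0017 × 5.164 = 10.34. Self-fit passes if observed audiologist-fit benefit is below 16.3 − 10.34 = 5.96. At SD 15 the limit is 16.3 − 7.75 = 8.55, and at SD 25 it is 16.3 − 12.92 = 3.38.

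**Step 2: probability of declaring non-inferiority.** P = 1 − F(2.0017), where F is the non-central t distribution with 58 df and non-centrality (16.3 − B) / [SD × √(2/30)]. For B = 5 and SD 20 the non-centrality is 11.3 / 5.164 = 2.188, so P = 57.6%.

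| True audiologist-fit benefit | SD 15 | SD 20 | SD 25 |
|---|---|---|---|
| 5 | 82% | 58% | 41% |
| 10 | 36% | 22% | 16% |
| 16.3 | 2.5% | 2.5% | 2.5% |
| 20 | 0.2% | 0.4% | 0.6% |

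**Step 3: other readings of the plan.** If the inequality in section 4.3 is applied to the point estimate alone, the figures at B = 10 are 95%, 89% and 84%, and at B = 16.3 they are 50%. If a non-significant t-test is taken as success, B = 10 passes in 28%, 52% and 67%.

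**Step 4: adding a within-arm check.** Also require the lower 95% limit of self-fit benefit (unaided minus aided) to exceed 0. By simulation, the B = 5 and B = 10 rows fall to about 2%, provided that scores do not shift for reasons other than the device. If both arms shift by 10 points for such reasons, self-fit adds nothing and audiologist-fit is 5 points better, both conditions are met in 80%, 53% and 34% of trials.

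**Step 5: power of the joint claim.** With equal true benefit in both arms:
- 15 points, SD 20: about 87% with or without the check.
- 10 points, SD 20: about 87% falls to 72%.
- 10 points, SD 25: 70% falls to 50%.

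**The case against.** The objective in section 3.1 is comparative: self-fit against a gold-standard audiologist fit. A reader might infer that the trial fails its stated objective because it does not prove absolute benefit. The documents do not support that; a benefit criterion goes beyond the comparison that the plan set out to make.

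A reader might also infer that the control is handicapped, because Phase I allows "no fine-tuning by the audiologist in the AF group". Section 3.2.2 withholds help from both arms in that phase, explains that this isolates the effect of the fitting, and allows audiologist fine-tuning in Phase II. The hypothesis covers both time points, so this is not evidence of a weakened control.

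The worst case is also demanding. Both arms wear the same device, and the self-fit algorithm is itself based on NAL-NL2 (sections 3.2.1 and 3.2.2), yet self-fit must give nothing while audiologist fitting helps. The margin has an anchor of a kind, and section 5.3 already makes each arm's benefit score available for reporting.

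All of this limits the point. It does not supply a decision rule, a link between the margin and control benefit, or a condition on how non-inferiority may be interpreted.

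**Conclusion.** The point holds in a conditional form. The text establishes that the margin is called arbitrary, that it is not related to audiologist-fit benefit, that no confidence limit is compared with it, and that no criterion concerns benefit over unaided hearing.

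The size depends on assumptions that the documents cannot settle: the SD, the control benefit and the decision rule. The risk is material if audiologist-fit benefit is about 10 points or less, and very small at 16.3 or more under a confidence-limit rule. A reader might infer that this trial is likely to pass an ineffective device. The documents do not support that, because they give no expected control benefit. For the same reason, the plan cannot exclude it.

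Nor does a test against unaided baseline settle the matter. The trial is unblinded and self-reported and has no untreated arm, so the reduction to about 2% depends on there being no non-device change.

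**What to change.** In sections 4.3 and 5.3:

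1. Name the APHAB score that is primary. State that non-inferiority is concluded at a given time point (2 weeks, 6 weeks) only if the lower limit of the two-sided 95% CI for the difference in mean benefit on that score, self-fit minus audiologist-fit, is above −16.3.
2. At the same time point and on the same score, report each arm's mean benefit (unaided minus aided) with its 95% CI. Do not interpret non-inferiority as evidence of effectiveness unless the lower limit for self-fit is above 0.
3. Report the confidence limit of the difference relative to the audiologist-fit benefit.
4. State that 16.3 was not derived from a group-level important difference.

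This changes wording only: the unaided APHAB is already collected, and no patients or visits are added. The cost is lower power for the joint claim when true benefit is small, as shown in step 5 of the working; at 15 points and SD 20 there is almost no loss. The report should say that the within-arm check is a minimum safeguard which cannot exclude placebo or expectation effects.
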